#### **10.4. Subgroup Analyses**

Due to the limited number of participants, we will conduct only a single subgroup analysis by evaluating the results in participants with and without diabetes. Since diabetes is relatively common in kidney transplant recipients and may be a dominant factor affecting SAF in these people, it would be important to investigate whether a low AGE diet is effective in people with diabetes.

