### **7.3. The Randomisation Scheme**

Participants will be randomised in an unrestricted 1:1 ratio in random varying block sizes using a computer-generated random number into two groups: a) standard diet (control group) or b) low

AGE diet (intervention group). Advice regarding both diets will be provided by an experienced dietitian. Both groups will receive precise oral and written instructions on how to follow the diets. Dietary advice will be individualised to patients' food preferences.

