### **10.1. Sample Size Calculation**

As this is a feasibility RCT, no formal sample size calculation is required; however, the aim will be to recruit 40 kidney transplant recipients to test the study procedures and the feasibility of delivering the intervention. Power calculation using ClinCalc indicates that, assuming an SAF value of  $2.81 \pm 0.64$  AU in the control group (Crowley et al., 2013), having a sample size of 18 in each group would give 80% power ( $\alpha=0.05$ ) to detect a difference in SAF of 0.6 AU between the groups at 6 months. The proposed recruitment would achieve this and allow for 10% drop-out.

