#### **10.3.2. Outcome Analysis**

Summary measures of all baseline variables will be calculated and reported. Primary and secondary outcomes will be compared between the two groups (Low AGE Diet vs. Standard Diet) at 6 months using a t-test if data are normally distributed or a Mann Whitney U test if not. Analysis will be by intention to treat.

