#### **10.5. Adjusted analyses**

As this is a feasibility study, we do not plan to conduct adjusted analyses.

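### The diabetes subgroup analysis reads naturally as one arm comparison per stratum, which cannot show whether the diet's effect differs; report the arm-by-diabetes interaction with its confidence interval, as exploratory

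*Combined protocol and SAP*

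**What the plan says.** Section 10.4 (Subgroup Analyses) limits the trial to one subgroup factor because numbers are small: "we will conduct only a single subgroup analysis by evaluating the results in participants with and without diabetes". It gives the purpose as follows: "it would be important to investigate whether a low AGE diet is effective in people with diabetes". It also describes diabetes as possibly a dominant influence on SAF.

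Section 10.3.2 (Outcome Analysis) compares the arms "at 6 months using a t-test if data are normally distributed or a Mann Whitney U test if not". The opening of section 10 names the same tests, and chi-square or Fisher's exact test for categorical variables. Section 10.5 (Adjusted analyses) states: "As this is a feasibility study, we do not plan to conduct adjusted analyses".

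No section names an interaction estimate, a confidence interval for the difference between strata, an exploratory label for the subgroup, or a rule for reading its results. Section 7.3 names no stratification factor for randomisation.

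**The concern.** The question in section 10.4 is about efficacy within one stratum. Together with sections 10.3.2 and 10.5, it points to a test of arms among participants with diabetes and another among those without. Whether the effect differs is a separate question, answered by the difference between the two stratum effects and its standard error. Setting one p-value beside another does not answer it, because the strata can differ in significance only through size and chance.

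Section 3.1 wants effect estimates to inform a larger trial, and section 13.1 foresees a grant application for one. A chance finding that the diet works without diabetes but is not shown to work with it could wrongly shape that trial's eligibility, stratification or sample size.

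**Working it through.** **Inputs.** From section 10.1: SD 0.64 AU, difference 0.6 AU, alpha 0.05, 18 evaluable per arm, 40 recruited with 10% drop-out. Sidedness is not stated; two-sided is assumed. The documents do not give the share with diabetes, so I assume 4, 5, 6 or 9 of 18 per arm (22% to 50%), equal in both arms.

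**The plan's own figure.** n per arm = 2 × (1.960 + 0.842)² × 0.64² / 0.6² = 17.9, which rounds up to 18. Also 40 × 0.9 = 36 = 2 × 18. The stated figure reproduces (power 80.3% by the normal formula, 78.0% by the noncentral t).

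**Separate tests when the effect is 0.6 AU in both strata.** The standardised effect is 0.6/0.64 = 0.9375. Power in a stratum with m per arm comes from the noncentral t with 2m − 2 df and noncentrality 0.9375 × √(m/2). Write P₁ for power with diabetes and P₀ for power without. The strata are independent, so:

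- P(significant only without diabetes) = P₀ × (1 − P₁)
- P(exactly one significant) = P₀ × (1 − P₁) + P₁ × (1 − P₀)

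At 5/13 per arm: 0.631 × 0.742 = 0.468; 0.258 × 0.369 = 0.095; total 0.563.

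| Diabetes / no diabetes per arm | Power with | Power without | Significant only without | Exactly one significant |
|---|---|---|---|---|
| 4/14 | 20% | 67% | 53% | 60% |
| 5/13 | 26% | 63% | 47% | 56% |
| 6/12 | 31% | 59% | 41% | 53% |
| 9/9 | 46% | 46% | 25% | 50% |

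Simulation with 100,000 trials per split agrees to within half a percentage point.

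**Smaller common effects.** The chance of exactly one significant stratum, across the four splits, is:

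- 0.4 AU: 36–39%
- 0.3 AU: 26–27%
- 0.2 AU: 17–18%
- no effect: 2 × 0.05 × 0.95 = 9.5%

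At 5/13, significance only without diabetes falls from 47% at 0.6 AU to 29% at 0.4 AU, 19% at 0.3 AU and 11% at 0.2 AU.

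**What an interaction estimate would deliver.** Without baseline SAF, SE = 0.64 × √(2/a + 2/b), with a and b the numbers per arm with and without diabetes. At 5/13: 0.64 × √(0.400 + 0.154) = 0.476. The 95% half-width is t(32) × SE = 2.037 × 0.476 = 0.97 AU.

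| Split | SE (AU) | 95% half-width (AU) | Power for a 0.6 AU interaction |
|---|---|---|---|
| 4/14 | 0.51 | 1.05 | 21% |
| 5/13 | 0.48 | 0.97 | 23% |
| 6/12 | 0.45 | 0.92 | 25% |
| 9/9 | 0.43 | 0.87 | 28% |

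Adding baseline SAF multiplies the SE by about √(1 − r²), where r is the correlation between baseline and 6-month SAF. The documents give no r. For an assumed 0.5 to 0.8 at 5/13, with t(31) = 2.04, the half-width is 2.04 × 0.476 × 0.866 = 0.84 down to 2.04 × 0.476 × 0.6 = 0.58 AU.

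**The case against.** **Separate testing is inferred.** Section 10.4 names no test, p-value or comparison of verdicts. This stands as a limit on the point. It is still the natural reading, since no other between-arm method for SAF is offered and adjusted models are excluded.

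**A reader might infer that the plan will probably produce a false difference.** The documents do not support that. The 50–60% figure needs a true effect of 0.6 AU in everyone, and section 10.1 uses 0.6 AU as the difference the trial could detect, not as an expected effect. At 0.3 AU the figure is about a quarter. The directional error also depends on the assumed share with diabetes, which section 10.4 describes only as fairly common; at an even split it is 25%.

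**A reader might also infer that the main comparison is biased** because "we do not plan to conduct adjusted analyses" and randomisation is not stratified by diabetes. That does not follow. With an assumed 8 to 14 participants with diabetes among 40, the chance that the arms differ by at least 4 is 24–32%. But randomisation keeps the unadjusted test valid, and the baseline summaries by arm in section 10.3.1 would show an imbalance. Four extra among 20 is 20 percentage points. If diabetes raised SAF by 0.2–0.6 AU (an assumption), the shift would be 0.04–0.12 AU, against a standard error of 0.64 × √(2/18) = 0.21 AU. Adjusting for diabetes is a choice about precision.

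**The interaction adds little in a feasibility study.** It is indeed imprecise, and labelling the subgroup exploratory with estimates and intervals would by itself remove much of the harm. The wide interval is nevertheless useful: it shows openly that the data cannot separate the strata, which two p-values conceal.

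**Conclusion.** The point holds as one of analysis and interpretation. The plan asks a within-stratum efficacy question, provides nothing that estimates the difference between strata, and sets no rule for reading the result. At the plan's own design values, judging each stratum by its own p-value gives discordant verdicts in about half to three-fifths of trials although the effect is the same in both. With smaller effects the risk is lower, down to 9.5% with none.

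This rests on 36 evaluable participants, SD 0.64 AU in both strata, two-sided 5% tests, an assumed 4 to 9 participants with diabetes per arm, and each stratum being judged by its own test. The sample size and the validity of the main comparison are unaffected. The change is worth making because it is cheap and the results are meant to inform a larger trial.

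**What to change.** In section 10.4, replace the separate evaluations with one linear model for 6-month SAF containing arm, baseline SAF, diabetes and arm-by-diabetes. Then specify that:

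- the interaction is reported with its 95% CI and labelled exploratory;
- stratum-specific effects are given with CIs, descriptively;
- no efficacy conclusion is drawn from a within-stratum p-value;
- a non-significant interaction does not show equal effects.

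Add a matching exception to section 10.5.

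**Cost.** Revised wording and one model; section 7.4 already collects diabetes history and baseline SAF. The downside is a visibly imprecise interaction: half-width about 0.87–1.05 AU without baseline SAF, perhaps 0.6–0.85 AU at 5/13 with it, and power of only 21–28% for a 0.6 AU interaction without it.

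Including diabetes as a covariate in the main comparison would be a secondary gain in precision. Stratifying randomisation by diabetes is optional and not needed for this point.

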#### **10.5. Adjusted analyses**

As this is a feasibility study, we do not plan to conduct adjusted analyses.

#### **10.6. Interim Analysis and Criteria for the Premature Termination of the Study**

As this is a feasibility study with minimal risk of harm, we do not plan to conduct an interim analysis.

The Sponsor may suspend or prematurely terminate either the entire study, or the study at an individual site, for significant reasons that must be documented (e.g. an unacceptable risk to participants or serious repeated deviations from the protocol/regulations). If this occurs, the Sponsor shall justify its decision in writing and will promptly inform any relevant parties (i.e. participants, investigators, participating sites, REC, regulatory bodies).

#### **10.7. Analysis Groups**

The two groups for analysis will be the Low AGE diet and Standard diet groups. Analyses will be by intention to treat and will include all participants who were randomised and received at least one session of dietary counselling regarding their diet (all-treated population).

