#### **Low AGE diet (intervention group)**

The low AGE diet will be the same as the standard diet in terms of calories (i.e. 30-35 kcal/kg/day) and protein (0.75-0.84 g/kg/day). However, it will reduce the dietary AGE content by changing cooking methods in food preparation to avoid exposure to dry heat such as frying, broiling, grilling and roasting, and to favour cooking with lower temperatures and high-water content as in stewing, steaming, boiling and poaching. In addition, the low-AGE group will be instructed to choose foods with low content of AGEs based on a food choice list that will contain examples of foods commonly available in the UK to be chosen as "allowed," "moderate intake," or "occasional." The goal will be to reduce dietary AGE intake to less than 8000 kU/day.

Dietary advice will be provided in person by an investigator with training and previous experience as a dietitian. Adherence to diets will be evaluated by means of a 3-day food diary (2 weekdays and 1 weekend day) every month. Monthly forms and written instructions on how to complete the 3-day food diaries will be sent by post to the participants. We will ask participants to return the completed food diaries in a pre-paid envelope. If needed, supplementary relevant diet information will be obtained by telephone consultation once the food diaries have been recorded and returned to the research dietitian.

There will be a follow-up meeting or discussion by telephone with participants randomised to the intervention group after 2 weeks of starting the study in order to reinforce the adherence and understanding of the intervention.

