##### **7.3.1. Method of Implementing the Allocation Sequence**

The system to be used to coordinate randomisation is [www.sealed envelope.com](http://www.sealedenvelope.com)

The Chief Investigator, [name] and [name] [name] will be aware of allocation which will be documented in the CRF (paper).

There is no expectation that randomisation codes will need to be accessed out-of-hours or in an emergency.

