## 7.5. Schedule of Assessments

Study Procedures/Assessments	Screening	Recruitment	Baseline	Months						Post-intervention
				1	2	3	4	5	6	
Eligibility assessment	x									
Study discussed and PIS given		x								
Informed consent		x								
Randomisation		x								
Participant characteristics			x							
Skin autofluorescence	x		x		x				x	
Routine blood tests			x		x				x	
3-day food diaries			x	x	x	x	x	x	x	
Dietary AGE food frequency questionnaire			x		x				x	
Subjective Global Assessment			x		x				x	
Handgrip strength			x		x				x	
Anthropometric measurements			x		x				x	
Cardiovascular evaluation			x		x				x	
Quality of life questionnaire (EQ-5D-5L)			x		x				x	
Treatment adherence				x	x	x	x	x	x	
Qualitative study interviews										x
Adverse event assessments				x	x	x	x	x	x	
Physician's Withdrawal Checklist				x	x	x	x	x	x	

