## 7.6. Withdrawal Criteria

Participants will be withdrawn from the study if they withdraw their consent at any point or decline to comply with the dietetic intervention or develop malnutrition. Female participants will be withdrawn from the study if they become pregnant.

Participants may be withdrawn from the study either at their own request or at the discretion of the Investigator. The participants will be made aware that this will not affect their future care. Participants will be made aware (via the information sheet and consent form) that should they withdraw the data collected to date cannot be erased and will be used in the final analysis.

If participants fail to attend for their study visits, a member of the research team will try to contact them by telephone within 24 hours of their appointment and by written correspondence within a week of the missed appointment. Multiple attempts at contact will be made by the research team over a period of a month before stating that a participant has been lost to follow-up.

Data that is collected prior to withdrawal will be kept and analysed as part of the data set. The date, time and reason for participant withdrawal will be documented on the case report form (CRF).

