### **10.3. Statistical Analysis**

#### **10.3.1. Summary of Baseline Data and Flow of Patients**

Descriptive statistics will be presented to summarize the distribution of baseline variables across each of the randomisation groups. The continuous baseline variables (e.g. SAF, age, height, weight and blood pressure) will be reported with means and standard deviations, if shown to be normally distributed, using a combined skewness and kurtosis test, otherwise will be reported with medians and Interquartile Ranges (IQR). The categorical variables (e.g. sex, ethnicity and employment status) will be reported with frequencies and percentages.

A Consolidated Standards of Reporting Trials (CONSORT) flow diagram will be produced, showing the frequency of patients/participants:

- Assessed for eligibility or found eligible,
- Excluded before randomisation (and the frequency of each reason for exclusion),
- Randomised,

- Allocated to each randomisation group,
- That received each allocated intervention,
- That did not receive each allocated intervention,
- Lost to follow-up (and the frequency of each reason for loss to follow-up) for each randomisation group,
- Analysed for each randomisation group,
- Not analysed (and the frequency of each reason for not being analysed) for each randomisation group.

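### Section 10.7 labels the analysis intention to treat but excludes anyone randomised who is lost before the first counselling session

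*Combined protocol and SAP*

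**What the plan says.** Section 10.3.2 (Outcome Analysis) states: "Analysis will be by intention to treat". Section 10.7 (Analysis Groups) repeats the label and then says the analyses "will include all participants who were randomised and received at least one session of dietary counselling regarding their diet (all-treated population"). No other analysis set is defined, and no analysis of everyone randomised is planned, even as a sensitivity analysis.

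Four other parts of the protocol bear on this:

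- **Allocation.** Section 7.3.1 says that the Chief Investigator and other named staff "will be aware of allocation which will be documented in the CRF (paper"). No blinding of participants or assessors is described. Both arms get dietary advice (Section 7.3: "Both groups will receive precise oral and written instructions on how to follow the diets"), and the content differs visibly between arms.
- **Participant flow.** The CONSORT list in Section 10.3.1 includes, by arm, a count headed "That did not receive each allocated intervention", as well as those not analysed, with reasons.
- **Withdrawal.** Section 7.6 withdraws participants who "decline to comply with the dietetic intervention or develop malnutrition". Data gathered before withdrawal are kept and analysed.
- **Missing data.** Section 10.8 leaves missing values out and rules out multiple imputation.

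**The concern.** An intention-to-treat set is fixed at randomisation. The set in Section 10.7 is fixed later, by whether a counselling session took place. A person lost in between is outside the analysis by definition, whether or not a 6-month SAF could be obtained. This differs from a missing value, which Section 10.8 already covers.

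If loss before counselling is related both to the arm and to SAF, the comparison of 6-month SAF no longer rests on the randomised groups. That comparison is the primary outcome, and Section 3.1 wants effect estimates from it to size a larger trial. Adherence is a secondary outcome compared in the same set, so its denominator can also lose people who never started.

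**Working it through.** **Inputs.** Section 10.1 gives a control SAF of 2.81 ± 0.64 AU, a target difference of 0.6 AU, 18 per group, 80% power, α = 0.05, 40 recruited and 10% drop-out. With 1:1 allocation (Section 7.3), 40 is 20 per arm. The documents give no figure for loss before counselling, so every loss below is an assumption.

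**1. The plan's own figure.** By the two-sided normal approximation, n = 2 × (1.960 + 0.842)² × 0.64² / 0.6² = 17.9, so 18 per group (power 80.3%). Then 36 / 0.90 = 40. The stated size reproduces and is not in dispute.

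**2. Who is excluded.** Reading 10.7 with 7.6 and 10.8:

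| Participant | In the 10.7 set? | 6-month SAF analysed? |
|---|---|---|
| Counselled, completes | Yes | Yes |
| Counselled, leaves later | Yes | Only if obtained |
| Randomised, not counselled, SAF obtained | No | No, excluded by rule |
| Randomised, not counselled, no SAF | No | No |

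Under an all-randomised definition the third row would be analysed. The fourth row changes only if the reading is actually sought.

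**3. Possible shift in one arm's mean.** Suppose k of 20 are lost before counselling in one arm only, and their SAF averages 1 SD above the full-arm mean. The retained mean then moves down by k × 0.64 / (20 − k).

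- k = 0: no shift.
- k = 1: 0.64 / 19 = 0.034 AU, and 0.034 / 0.6 = 6% of the target.
- k = 2: 1.28 / 18 = 0.071 AU, and 0.071 / 0.6 = 12% of the target.

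Loss from the low-AGE arm would exaggerate the benefit; the same loss from the standard arm would understate it. Equal loss of the same kind in both arms cancels.

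A wider range uses the difference D (in SDs) between the excluded and the retained members of the arm: shift = (k / 20) × D × 0.64. For k = 1 to 4 and D = 0.5 to 1, this runs from 0.016 to 0.128 AU, or 3% to 21% of 0.6 AU.

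**4. Against random error.** With 20 and 18 analysed, the standard error of the difference is 0.64 × √(1/20 + 1/18) = 0.208 AU. A shift of 0.071 AU is about a third of that.

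**5. Power.** With 20 and 18 analysed, power is 82.3% by the same approximation, above the planned 80%. Power is not the problem.

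**6. Adherence denominator.** Suppose 12 in an arm adhere and two of 20 were never counselled. Adherence is 12/18 = 67% in the all-treated set, and 12/20 = 60% if all randomised are counted and the two are classed as not adherent. If their adherence is instead treated as missing and left out under Section 10.8, the denominator stays at 18. The plan does not say which applies.

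**The case against.** The plan names its set all-treated in plain sight, the study has 40 participants and is about feasibility, and the counselling condition applies equally to both arms. The number lost before a first session may well be zero. Section 7.1.1 arranges one further visit for consent and baseline assessments, so randomisation and counselling may be close together. All of this stands, and it limits the size of the problem. It does not make the set intention to treat.

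A reader might draw four stronger conclusions, which the documents do not support:

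- **That everyone who leaves after allocation is dropped.** Only those lost before the first session are. Later leavers remain in the set and their earlier data are kept under Section 7.6.
- **That early refusals vanish from the feasibility results.** Section 3.1 lists dropout rates with reasons, and the flow diagram in 10.3.1 counts those not treated and not analysed by arm.
- **That participants will leave in reaction to their arm.** Section 7.3.1 shows only that staff know the allocation. Nothing says when participants learn it. The Section 7.5 schedule places randomisation under Recruitment, before Baseline, but has no row for counselling, so a gap is neither shown nor ruled out. If participants first learn their arm during the session, loss before it cannot be their reaction to it, although staff knowledge leaves some risk.
- **That rewording 10.7 alone would cure it.** Someone who refuses the diet before counselling could also be withdrawn under 7.6, would then have no 6-month SAF, and would be left out under 10.8 whatever 10.7 says.

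**Conclusion.** The label and the definition conflict, and this needs no assumption: it follows from Sections 10.3.2 and 10.7 as written. Bias in the 6-month SAF comparison is possible but not demonstrated. It needs loss before counselling that differs between arms and is related to SAF. For one or two leavers in one arm at 1 SD, the shift is 0.034 or 0.071 AU, small beside the standard error; the number and type of leavers are assumed. The adherence effect depends also on how uncounselled people would be classified. The point should be corrected because the rule is wrong as written and cheap to change, not because a large distortion is expected.

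**What to change.** - **Section 10.7.** Define the intention-to-treat set as all randomised participants, analysed in the arm allocated, whether or not they were counselled. Keep the all-treated set as a named sensitivity analysis without the intention-to-treat label. State how uncounselled participants count in the adherence outcome.
- **Section 7.6.** Reconcile it with that definition, so that the 6-month SAF is still sought from randomised participants who were not counselled or who decline the diet, unless they withdraw consent. This concerns outcome measurement only, not whether anyone should continue a diet.
- **Reporting.** Show losses before the first counselling session by arm in the flow diagram already planned.

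The cost is small text changes in 10.7 and 7.6, and a few extra SAF readings, each giving a result in 3 to 5 minutes (Section 7.1.1), at routine visits where possible. The estimate may be slightly diluted by people who received no counselling. The 18 per group and total of 40 do not change.
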